17.0 PROTOCOL REVISION HISTORY

Version #	Rationale for Change	Section or Page affected	Description of change
1.0	New Protocol		
2.0	Allow for visit 2 and 3 timing flexibility, no effect on data collection	Section 3.1 and 6.3	(up to 3 days after study period is completed)
2.1	Typo	Cover Page	Correct date for Version History for Version 1.0 August 16, 2017 to Version 1.0 August 7, 2017
2.2	Typo	Header	Corrected header and updated to Version 2.2 and corrected date
3.0	Update for visit 2 and 3 timing flexibility, no effect on data collection	Section 3.1 and 6.3	+/- 3 days, no fewer than 13 days and no more than 17 days
4.0	Non-insulin users use these 32G pen needles for non-insulin injections. Addition of 31G user with wash-in, to increase subject pool.	Section 1.0, 2.0, 3.0, 3.2.3, 4.0, 4.2, 4.3, 5.3, 6.0, 8.2	Added that non-insulin users only using pen needles for non-insulin injections could also be included in the study. The users needed a minimum of one injection of non-insulin per day. Added 31G users with a wash in who were willing to switch to a 32G for the period of the study.

Version #	Rationale for Change	Section or Page affected	Description of change
4.1	Formatting corrections	All	Formatting of Heading 2 was corrected.
5.0	
Broadened groups to allow wash-in of 32G x 4mm/5mm/6mm user to increase subject pool
 
Inclusion/Exclusion Criteria
	
Section 3.1
 
Section 4.0
	
Subjects using 32G under 6mm in length (such as BD Nano) could be washed-in to fill up other groups
 
Decrease in I/E Criteria from 6 months to 3 months for self- injecting with a pen injector and decrease from 3 months to 1 month for use with one of the competitor products

18.0 APPENDICES

The following appendices are attached:

AE	Adverse Events
BD	Becton Dickinson & Company
BG	Blood Glucose
BMI	Body Mass Index
CI	Confidence Interval
CRF	Case Report/ Record Form
FDA	Food and Drug Administration
G	Gauge
GCP	Good Clinical Practice
ICH	International Conference on Harmonization
INJ	Injection
ITT	Intent-to-treat
mm	Millimeter
NI	Non-Inferiority
PN	Pen Needle
PP	Per-Protocol
SAE	Serious Adverse Events
SD	Standard Deviation
VAS	Visual Analog Scale

2 Executive Summary

Summary statements will be made to show the results of both non-inferiority tests and the statistical conclusions per endpoint. Summary tables will also be provided.

3 Background and Study Description

3.1 Study Background

This study will be used to support the business replacement strategy for BD's current 4mm pen needle. A design improvement is being implemented by introducing a flatter hub (base) by eliminating the post on the hub. This study is designed to assess the User's experience and preference and outcomes are intended to be used for marketing claims. This study will have four study groups based on commercially available 32G pen needle groups: 1) BD Nano, 2) NovoFine, 3) NovoFine Plus & NovoTwist and 4) Other 32G (such as UltiMed, MHC, or other private label).

3.2 Study Objectives

3.2.1 Primary Objectives

For all study groups combined, compare user preference for the BD Nucleus pen needle vs. the subjects' current commercially available pen needle.

3.2.2 Secondary Objectives

1. For each individual study group, compare user preference for the BD Nucleus pen needle vs. the subjects' current commercially available pen needle.
2. For all study groups combined and each individual study group, compare the user experience with the BD Nucleus pen needle and the subjects' current commercially available pen needle for component preference.
 - (a) Outer Cover Handling
 - (b) Inner Shield Handling
 - (c) Hub Comfort
3. For all study groups combined and each individual study group, compare the user experience with the BD Nucleus pen needle and the subjects' current commercially available pen needle for the following:
 - (a) Overall Comfort
 - (b) Anxiety associated with a needle stick injury
 - (c) Injection Pain
 - (d) Bruising
 - (e) Bending
 - (f) Injection site Bleeding
 - (g) Ease of use
 - (h) Leakage from the injection site

3.2.3 Exploratory Objectives

1. For all study groups combined, assess the user acceptance for the following items for the pen needle (non-comparative):
 - (a) Teardrop Label Removal Force
 - (b) Outer Cover Removal Force
 - (c) Inner Shield Removal Force
 - (d) Ease of Insulin Delivery
2. For all study groups combined, Pen Needle breakage will be monitored.
3. A subgroup with Asian ethnicity and all study groups combined, will also be evaluated for the objectives listed in Primary and Secondary Objectives.

3.3 Study Design

This is a multi-site, prospective, open-label, randomized, 2-period crossover (15 days per period) study comparing commercially available 32G pen needles to the BD Nucleus pen needle. BD Nucleus will be compared to four groups of pen needles:

- Group 1: BD Nano (32Gx4mm)
- Group 2: NovoFine (32Gx6mm)
- Group 3: NovoFine Plus (32Gx4mm) & NovoTwist (32Gx5mm)
- Group 4: Other 32G (such as UltiMed, MHC, or other private label)

Approximately 25% of the subjects are expected to be Type 1 patients and the remaining 75% are expected to be Type 2 patients.

The study is targeting 260 subjects. A total of 240 subjects are needed with an additional 20 subjects for subjects lost to follow up or other significant protocol deviations. Each group will consist of approximately 60 subjects. Each subject will be screened to determine eligibility into the study. Subjects entering the study who are currently injecting with one of the above mentioned pen needles will automatically be enrolled in their respective group. For example, if a subject comes in using the BD Nano, they will be enrolled in Group 1. If their current pen needle group has completed enrollment, they will be eligible for wash-in (see below).

To facilitate recruitment, a 14 day wash-in period will be allowed in the following situations:

- As BD holds the vast majority of the Pen needle market share in the US, enrolling subjects using non BD brands will be difficult. Subjects currently using a 32G pen needle of 4, 5 or 6 mm lengths will be allowed to wash-in if their current pen needle group has completed enrollment of 60 evaluable subjects. These subjects will be eligible to wash-in to the next available applicable group, per the Wash-In randomization schedule. The length of their current pen needle will be maintained.

- For subjects currently using a 31G pen needle of 4, 5 or 6 mm lengths provided the subject is willing to switch to an assigned commercially available 32G pen needle for the duration of the study. These subjects will be eligible to wash-in to an available applicable group, per the Wash-In randomization schedule. The length of their current pen needle will be maintained.

Wash-in subjects will be randomized as follows (cf. Wash-in randomization schedule):

- If subject is currently on a 31G x 4mm or 32G x 4mm they will get randomized to either Group 3 (Novo Fine Plus (32Gx4mm)) or Group 4 (UltiCare Micro 32Gx4mm).
- If subject is currently on a 31G x 5mm or 32G x 5mm, they will randomized to either Group 3 (NovoTwist (32Gx5mm)) or Group 4 (MHC Easy Touch 5mm x 32G).
- If subject is currently on a 31G x 6mm or 32G x 6mm, they will randomized to either Group 2 (Novo Fine (32Gx6mm)) or Group 4 (Simple Diagnostics Comfort EZ 6mm x 32G).

Subjects who will remain on their current 32G pen needle will be required to visit the site a total of three times. Wash-in subjects will have an additional visit (Wash-in Visit) for a total of 4 visits (cf. Figure 1). Note that in the following document, “Current PN” and “Current/Assigned PN” are both used interchangeably to refer to the study arm where subjects did not use BD Nucleus PN.

The study will consist of two 15 day periods (± 3 days, no fewer than 13 days and no more than 17 days) in which the subject will use each pen needle (BD Nucleus pen needle or Commercially available 32G pen needle, order randomized) for injection.

Results will be compared to address the Primary, Secondary and Exploratory objectives. A final report will be issued summarizing all outcomes and conclusions.

Diagram 1 Subject Flow Chart

[figure not shown]

Figure 1: Subject Flow Chart

3.4 Endpoints

3.4.1 Primary Endpoints

Preference: At the end of the last study period, each subject will be asked to evaluate his or her perception using a 150mm relative VAS Scale. The question “Which pen needle did you prefer overall?” will be asked. The far left (-75mm) of the scale is labelled “Period 1 pen needle was *strongly* preferred

overall”, the 0mm center point is labelled “No preference” and the far right (+75mm) of the scale is labelled “Period 2 pen needle was *strongly* preferred overall”. The average rating will be used to assess non-inferiority and superiority.

3.4.2 Secondary Endpoints

- **Overall Comfort, Anxiety Associated with a Needle Stick Injury, Injection Pain, Ease of Use, Outer Cover Handling, Inner Shield Handling, Hub Comfort:** At the end of the last study period, each subject will be asked to evaluate his or her perception using a 150mm relative VAS scale. Average ratings will be used to assess non-inferiority and superiority.
- **Needle Bending or Injection Site Bleeding or Bruising:** After each injection, each subject will evaluate his/her perception of each by answering with a “Yes” or “No” response. The difference in percentage of “Yes” responses between the PNs will be used to assess non-inferiority.
- **Leakage:** After each injection leakage will be recorded using the scale below. Recorded leakage will be transformed to Yes/No scale and the difference in percentage of “Yes” responses between the PNs will be used to assess non-inferiority.

[figure not shown]

Figure 2: Subject Flow Chart

3.4.3 Exploratory Endpoints

At the end of each study study period, each subject will evaluate his or her perception of each of the following by answering with a Yes or No response:

- **Teardrop Label Removal Force:** The subject will be asked “Did you find the teardrop label easy to remove?”
- **Outer Cover Removal Force:** The subject will be asked “Did you find the outer cover easy to remove?”

- **Inner Shield Removal Force:** The subject will be asked “Did you find the inner shield easy to remove?”
- **Ease of Insulin Delivery:** The subject will be asked “Were you able to deliver the insulin easily?”

Needle Breaking: After each injection, each subject will evaluate his/her perception by answering with a “Yes” or “No” response. The difference in percentage of “Yes” responses between the PNs will be used as an endpoint.

3.4.4 Safety Endpoints

At second and third visits, presence and severity of any adverse events will be evaluated, recorded, and followed up as required.

3.5 Acceptance Criteria

3.5.1 Primary Objective

Non-Inferiority Criterion (based on relative VAS where -75mm is strongly preferred Current/Assigned and +75mm is strongly preferred Nucleus) is -10mm and the Superiority Criterion is 0mm.

3.5.2 Secondary Objectives

- Overall Comfort, Anxiety Associated with a Needle Stick Injury, Injection Pain, Ease of Use, Outer Cover Handling, Inner Shield Handling, Hub Comfort: Same as for primary objective
- Needle Breaking, Needle Bending, Injection Site Bleeding, Bruising and Leakage Score > 1: The difference in occurrence rate with BD Nucleus pen needle vs occurrence rate with Current pen needle will be compared to a 4% non-inferiority (NI) criteria.

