3.3 Acceptance Criteria

Primary Objective: Non-Inferiority Criterion (based on relative VAS where -75mm indicates a strong preference for Period 1 pen needle and +75mm indicates a strong preference for Period 2 pen needle) is -10mm.

Secondary Objectives:

For Overall Comfort, Anxiety Associated with a Needle Stick Injury, Injection Pain, and Ease of Use the Non-Inferiority Criterion is also -10mm.

For Needle Breaking, Needle Bending, Injection Site Bleeding, Bruising and Leakage Score > 1: The difference in occurrence rate with BD Nucleus pen needle vs Occurrence rate with Current pen needle will be compared to a 4% non-inferiority (NI) criteria.

Exploratory Objectives: No formal acceptance criteria has been established for this study.

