9.2 Adverse Event (AE) Management

At each study contact, subjects will be questioned in an open-ended manner regarding any new or worsening undesirable signs or symptoms they may have experienced since the previous contact. Elicited signs and symptoms must be comprehensively documented on the appropriate source documentation.

Each sign, symptom, disease or illness reported must be evaluated by the Investigator or designee to determine if it meets the definition of an Adverse Event.

The clinical course of the event will be followed according to accepted standards of medical practice until the event resolves, stabilizes, or in the opinion of the Investigator, is no longer considered clinically significant. The Investigator must supply the Sponsor with information concerning the follow up and/or resolution of the AE.

Some reported or observed signs and symptoms are inherent to subcutaneous injection and are likely to occur transiently for nearly all subjects in this study. Such signs or symptoms will not be considered AEs as long as they are mild (transient, easily tolerated, no interference with daily activities) and the Principal Investigator agrees. The following will not be considered AEs:

- Mild, self-limited pain, swelling at the injection site
- Mild bruising at the injection site
- Mild self-limited bleeding at the injection site

However, these signs and symptoms **must be considered AEs and** documented on the Adverse Event CRF should any of them occur in such a way that the extent or nature of the experience exceeds that normally associated with the procedure, as judged by the Subject to be excessive pain, bruising or bleeding.

All needle breaking **must be considered AEs and** documented on the Adverse Event CRF.

Some signs and symptoms are inherent to the conditions under study (i.e. diabetes) and are likely to occur transiently for nearly all subjects in this study. Episodes of hyperglycemia and hypoglycemia occurring after subject enrollment and exposure to study product and/or study procedures, should be reported based on the following criteria:

- All blood glucose values <50 mg/dL (hypoglycemia) or >400 mg/dL (hyperglycemia) that require 3rd party (defined as, assistance of another person to administer carbohydrates or glucagon) or medical assistance for recovery will be recorded as an AE and assessed for seriousness.

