3.5.3 Exploratory Objectives

No formal acceptance criteria.

4 Sample Size

Based on previous studies, SD for relative VAS is assumed to be 35mm. A sample size of 60 subjects per group has 90% power of passing a 10mm Non-Inferiority (NI) criteria, assuming a true average of 5mm in favor of Nucleus (2-sided 95% CI for the mean). A sample size of minimum 45 subjects per group is sufficient to provide at least 80% power (this lower sample size may be used for Group 2, Group 3 and Group 4). This sample size applies to each subgroup for which a NI (or superiority) claim is desired.

5 Intended Statistical Software

This document was generated with R version 3.3.2 (2016-10-31) and the following packages (version) were used: assertthat (0.1), base (3.3.2), BDbasics (0.1.11), colorspace (1.3.2), datasets (3.3.2), ggplot2 (2.2.0), graphics (3.3.2), grDevices (3.3.2), grid (3.3.2), gtable (0.2.0), lattice (0.20.34), lazyeval (0.2.0), magrittr (1.5), methods (3.3.2), munsell (0.4.3), nlme (3.1.128), plyr (1.8.4), Rcpp (0.12.13), reshape2 (1.4.2), rJava (0.9.8), scales (0.4.1), stats (3.3.2), stringi (1.1.2), stringr (1.1.0), tibble (1.2), tools (3.3.2), utils (3.3.2), xlsx (0.5.7), xlsxjars (0.6.1), xtable (1.8.2).

The study will be conducted within the same environment or more recent versions.

6 Data

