11.2.4 Exploratory Objectives

All binary responses will be summarized as in Section 11.2.2.

The difference in proportion of BD Nucleus vs. Current/Assigned Pen needle with a “Yes” response will be provided as in Table 7, but no criterion will be applied.

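### Needle breaking carries a 4% non-inferiority rule in Protocol 3.3, Protocol 13.3 and SAP 3.5.2, but is exploratory with no criterion in Protocol 2.3 and the rest of the SAP

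*SAP*

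**What the plan says.** **Breaking with a pass/fail rule.** Protocol 3.3, under secondary objectives, opens its 4% list "For Needle Breaking, Needle Bending, Injection Site Bleeding, Bruising and Leakage Score > 1". Protocol 13.3 names breaking among the outcomes analysed with a 95% score interval for the difference in proportions, and concludes non-inferiority if the upper bound is below 4%. Its leakage paragraph refers back to that analysis and names breaking again. SAP 3.5.2 has the same list: "Needle Breaking, Needle Bending, Injection Site Bleeding, Bruising and Leakage Score > 1: The difference in occurrence rate with BD Nucleus pen needle" against the current needle "will be compared to a 4% non-inferiority (NI) criteria". Protocol 3.2.2 lists breaking among the secondary endpoints but states no margin.

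**Breaking without a rule.** Protocol 2.3 places breakage under exploratory objectives, to be monitored with all groups combined; Protocol 2.2 includes bending but not breaking. SAP 3.2.3 agrees. SAP 3.4.3 lists it as an exploratory endpoint: "Needle Breaking: After each injection, each subject will evaluate his/her perception". SAP 3.5.3 says of exploratory objectives: "No formal acceptance criteria". The heading of SAP 7.2.2.2, the non-inferiority analysis, covers bending, bleeding and bruising only, and the heading of SAP 7.2.2.4 puts breaking with the exploratory analyses. SAP 11.2.4 says that the difference in proportions "will be provided as in Table 7, but no criterion will be applied".

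**Safety.** Protocol 9.2: "All needle breaking must be considered AEs and documented on the Adverse Event CRF".

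**The concern.** One outcome has two statuses, and each leads to a different sentence in the report. Under the first set of passages the report tests breaking and states whether the new needle is non-inferior. Under the second it gives proportions and a difference, and draws no conclusion. Protocol 1.0 and SAP 3.1 say that the outcomes are meant for marketing claims, so whether a non-inferiority statement on breaking exists has consequences.

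The 4% margin is also the one used for bruising and bleeding. Protocol 9.2 exempts mild forms of those two from adverse event reporting but makes every break an adverse event. Neither document explains why one margin should serve both kinds of outcome, so it is worth knowing how many breaks the rule would let through.

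**Working it through.** **1. The passages side by side**

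| | Secondary, or 4% rule | Exploratory, no rule |
|---|---|---|
| Protocol | 3.2.2 (status only), 3.3, 13.3 | 2.3; 3.3 gives exploratory objectives no criterion |
| SAP | 3.5.2; example code in 7.2.2.2 | 3.2.3, 3.4.3, 3.5.3, heading of 7.2.2.2, 7.2.2.4, 11.2.4 |

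Both documents are split internally. In the SAP, 3.5.2 and 3.5.3 are consecutive sections. The SAP 7.2.2.2 code tests a variable named `Break` and comments that an upper bound below 0.04 satisfies non-inferiority, although that section's heading leaves breaking out.

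**2. Reproducing the SAP's interval**

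Write p1 = x1/n1 for Nucleus, p2 = x2/n2 for the comparator and N = n1 + n2. The upper score limit is the value d that solves

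(p1 − p2 − d) / √{[p̃1(1 − p̃1)/n1 + p̃2(1 − p̃2)/n2] × N/(N − 1)} = −1.96,

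where p̃1 = p̃2 + d are the maximum likelihood estimates under that constraint. For the SAP example (45/825 versus 56/866) this gives −0.01012 (−0.03303, 0.01273), as printed in SAP 7.2.2.2. The four rows of Table 7 also reproduce to rounding.

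**3. The largest break count that still passes**

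Inputs from the documents:
- about 60 subjects per group (Protocol 3.1), or a minimum of 45 for Groups 2 to 4 (SAP 4)
- 15 days per needle (Protocol 3.1)
- one Yes/No answer per injection (SAP 3.4.3)
- injections as the denominator (SAP Tables 5 and 7)

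Assumptions, because the documents give neither figure: 1 to 4 injections a day, and no comparator breaks.

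Injections per needle, n = subjects × 15 × injections per day. With x2 = 0 and equal n, the constrained estimates are p̃2 = 0 and p̃1 = d. The equation becomes

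(1 + k)d² − (2p + k)d + p² = 0, with p = x/n and k = (1.96²/n) × 2n/(2n − 1),

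and the upper limit is the larger root.

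Example, n = 900 and x = 24: p = 0.026667, k = 0.004271, 2p + k = 0.057604. Then d = [0.057604 + √(0.0033182 − 0.0028566)] / 2.008541 = 0.0394, which passes. With x = 25 the limit is 4.07%, which fails.

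| Subjects × days × injections/day | n per needle | Largest passing x | Observed | Upper limit | Limit at x + 1 |
|---|---|---|---|---|---|
| 45 × 15 × 1 | 675 | 17 | 2.52% | 3.997% | 4.18% |
| 60 × 15 × 1 | 900 | 24 | 2.67% | 3.94% | 4.07% |
| 60 × 15 × 2 | 1,800 | 55 | 3.06% | 3.96% | 4.02% |
| 60 × 15 × 3 | 2,700 | 88 | 3.26% | 3.998% | 4.04% |
| 60 × 15 × 4 | 3,600 | 120 | 3.33% | 3.97% | 4.001% |

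**4. Dependence on the denominator**

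If the unit were the subject, one break against none would fail within a group: the upper limit is 8.9% at n = 60 and 11.6% at n = 45. The counts in step 3 therefore hold only for the per-injection reading, which is the one used in the SAP tables. Protocol 3.3 and SAP 3.5.2 speak only of an occurrence rate.

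**The case against.** The strongest reply is that the SAP governs and that its working sections agree. Protocol 13.0 leaves the methods to the SAP and requires deviations to be justified and described. SAP 7.2.2.4 and 11.2.4 treat breaking as exploratory. The SAP 3.5.2 bullet looks like text carried over from Protocol 3.3: it still has the leakage cut-off above 1, whereas SAP 7.1.2 and 7.2.2.3 use above 0. This carries weight. A reader might infer that the analyst is free to choose after seeing the data, and the documents do not go that far. But the SAP has no precedence clause, and its own 3.5.2 and example code point the other way, so the conflict needs correcting.

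Three other stronger readings also fail:
- *An observed 4-point excess of breaks would pass.* It would not. The upper bound must be below 4%, and in the cases above passing stops at 2.5% to 3.3% observed.
- *The passing break rates are unacceptable on safety grounds.* Neither document gives an expected or tolerable break rate, so this cannot be said from them.
- *Breaks would go unseen.* They would not. Each is an adverse event, and Protocol 13.5 and SAP 8 list these events and summarise them by needle and group.

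It is also fair to say that no comparator breaks is an extreme scenario, and that the interval treats injections by one subject as independent. An interval that allowed for clustering would usually be wider and pass fewer breaks. The counts describe the rule as the plan states it; they do not predict the result.

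**Conclusion.** The inconsistency stands in the current text of both documents and should be reconciled before analysis. It affects whether a non-inferiority conclusion on breaking is drawn; the capture of events is not affected.

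If the 4% rule were applied as the SAP applies it to the other diary outcomes, one group could pass with 24 to 88 Nucleus breaks against none (60 subjects, 1 to 3 injections a day), or with 17 (45 subjects, one a day). These figures rest on the injection denominator, independent injections, no comparator breaks and the assumed injection frequencies. The contradiction itself rests on none of them.

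**What to change.** Make breaking exploratory and safety-related throughout, with no pass/fail conclusion:
- Protocol 3.3 and SAP 3.5.2: delete needle breaking from the 4% list.
- Protocol 13.3: delete it from the non-inferiority analysis and from the cross-reference in the leakage paragraph.
- Protocol 3.2.2: move it from the secondary to the exploratory endpoints (3.2.3).
- SAP 7.2.2.2: rename the `Break` variable in the example code after an outcome that the section covers.

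No new analysis is needed. SAP 11.2.4, through 11.2.2, already gives breaks per injection with a 95% interval and the percentage of subjects with at least one event. Present these beside the adverse event listing.

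The cost is wording in two documents, and the sponsor gives up a non-inferiority statement on needle breaking.
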